Finally, in July 2018, tofacitinib 5 mg tablet BID and 10 mg tablet BID were approved by the EC for the treatment of moderately-to-severely active ulcerative colitis (UC) in patients with inadequate response, loss of response or intolerance to conventional therapy or a biologic agent. UC is a bowel disease characterised by inflammation and ulcers in the colon and rectum. In clinical trials, patients treated with 5 mg or 10 mg of tofacitinib BID were more likely to achieve and/or maintain a clinical response and remission of their condition as compared to patients in the placebo group.³ At the time of initial approval, the doses of tofacitinib for the treatment of moderately-to-severely active UC were 10 mg BID for induction (up to a 16-week period) and 5 mg BID for maintenance, which should not be exceeded.⁴

Table 1 summarises the date to facitinib was approved by the EC and the approved dose for each of the 3 approved indications.

Table 1. Summary of approved indications and dosages for tofacitinib

Indication	Date approved by the EC	Approved dose
RA	March 2017	5 mg immediate-release tablets BID
	December 2019	11 mg prolonged-release tablets QD
PsA	June 2018	5 mg immediate-release tablets BID
	July 2021	11 mg prolonged-release tablets QD
UC	July 2018	5 mg and 10 mg immediate- release tablets BID

Note: BID is an abbreviation for "bis in die," which in Latin means twice a day; QD is an abbreviation for "quaque die," which in Latin means once a day

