Concomitant use of a contraindicated potent immunosuppressants	Comedication	Defined as ≥30 overlapping days' supply of a tofacitinib prescription dispensing and a prescription dispensing for a contraindicated potent immunosuppressants (as identified by ATC code[s]) during the follow-up period. Days of supply in SNDS will be approximated by reimbursed package size and per recommended posology. Duration of tofacitinib therapy defined in Section 9.3.2.
Concomitant use of MTX	Comedication	Defined as ≥30 overlapping days' supply of a tofacitinib prescription dispensing and a prescription dispensing for MTX during the follow-up period.
Concomitant use of a corticosteroid	Comedication	Defined as ≥30 overlapping days' supply of a tofacitinib prescription dispensing and a prescription dispensing for a corticosteroid (as identified by ATC code[s]) during the follow-up period.
Concomitant use of anti-TB therapy	Comedication	Defined as ≥30 overlapping days' supply of a tofacitinib prescription dispensing and a prescription dispensing for anti-TB therapy (as identified by ATC code[s]) during the follow-up period.

Table 3. Operational definitions of study variables in Système National des Données de Santé

Variable	Role	Operational definition
Primary Objective 2: Pr	escribers' adherenc	e to the tofacitinib aRMMs
		per indication and duration of use
Duration of tofacitinib	Outcome:	Defined in Section 9.3.2. Assessed during the follow-up
therapy	Adherence to	period.
	recommended	
	posology	
ADD	Outcome:	Defined in Section 9.3.3. Assessed during the follow-up
	Adherence to	period.
	recommended	
	posology	
A patient with an	Outcome:	Among RA/PsA patients is defined as 0 ICD-10 diagnosis
ADD of >11 mg	Adherence to	code for UC during baseline or follow-up period and an
during any of the 8-	recommended	ADD of >11 mg during any of the 8-week intervals.
week intervals and no	posology	
evidence of a		
diagnosis for UC		
A patient with an	Outcome:	Among UC patients, is defined as ≥ 1 prescription dispensing
ADD of ≥15 mg in	Adherence to	for a biologic (as identified by ATC codes) prior to the index
Weeks 17-24, Weeks	recommended	tofacitinib dispensing and an ADD ≥15 mg in any of the
25-32, Weeks 33-40 or	posology	intervals: Weeks 17-24, Weeks 25-32, Weeks 33-40 or
Weeks 41-48 of		Weeks 41-48 of follow-up.
follow-up and with		Complete list of biologics in ANNEX 7. LIST OF ATC
evidence of a		CODES FOR MEDICATIONS OF INTEREST TO AVOID
diagnosis for UC but		WHILE TAKING TOFACITINIB

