no use of an		Note: This definition will miss those who have one 10 mg
alternative therapy		BID prescription and the remaining prescriptions are 5 mg
(i.e., biologic) prior to		BID.
tofacitinib initiation		
A patient who has	Outcome:	Among UC patients, is defined as ≥ 1 prescription dispensing
known VTE, CV or	Adherence to	for a biologic (as identified by ATC codes) prior to the index
malignancy risk	recommended	tofacitinib dispensing and an ADD >10 mg in any of the
factors with an ADD	posology	intervals: Weeks 17-24, Weeks 25-32, Weeks 33-40 or
of >10 mg in Weeks		Weeks 41-48 of follow-up and ≥1 VTE, CV or malignancy
17-24, Weeks 25-32,		risk factors from baseline to Week 16.
Weeks 33-40 or		
Weeks 41-48 of		An ADD \geq 15 mg in the definition above will be used in a
follow-up and with		sensitivity analysis.
evidence of a		
diagnosis for UC but		
no use of an		
alternative therapy		
(i.e., biologic) prior to		
tofacitinib initiation		

Adherence to patient screening and laboratory monitoring prior to and during tofacitinib treatment

The following recommended screenings and monitoring will be assessed in the following time frames:

- In the 30 days prior to and including the day of tofacitinib initiation;
- In the 31 to 60 days prior to tofacitinib initiation;

Table 3. Operational definitions of study variables in Système National des Données de Santé

Donnees de Sante			Donnees	
	Variable	Role		Operational definition

- In the 61 to 90 days prior to tofacitinib initiation; and
- In the 91 to 180 days prior to tofacitinib initiation;

For patients with at least 6 months of tofacitinib therapy (duration of tofacitinib therapy defined in Section 9.3.2):

- In the 60 days after the day of tofacitinib initiation;
- In the 61 to 120 days after tofacitinib initiation; and
- In the 121 to 180 days after to facitini binitiation.

For patients with 12 months of tofacitinib therapy (duration of tofacitinib therapy defined in Section 9.3.2):

- In the 181 to 240 days after tofacitinib initiation;
- In the 241 to 300 days after to facitinib initiation; and
- In the 301 to 360 days after to facitinib initiation.

For analyses, 1 month will be defined as 30 days and 1 year will be defined as 360 days.

List of laboratory codes in ANNEX 10. LIST OF LABORATORY TEST CODES.

List of laboratory codes	III THI TILL TO. LIDT	OF EMBORITORY TEST CODES.
Creatinine (serum or	Outcome:	Defined as ≥1 procedure code or ≥1 ICD-10 diagnosis code

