9.3.3. Average daily dose

Drug reimbursement data will be utilised to estimate tofacitinib ADD (in mg per day) for each patient and duration of treatment. ADD will be described in each 8-week period, based on the posology and recommended duration of use in the SmPC, during the follow-up period for a total of six 8-week periods.

ADD will be calculated by total dose dispensed during an 8-week period divided by the length of the 8-week period, 56 days. Dose per prescription will be determined by the dose per tablet multiplied by the number tablets on packaging. Total dose dispensed is the sum of doses from all prescriptions in an 8-week period. If a prescription spans across 2 or more 8-week periods, the dose of the prescription will be prorated across periods.

ADD will be calculated from Week 1 through Week 48. For each 8-week period, ADD will be described as a continuous and categorical variable as below:

- Up to 5 mg ADD;
- >5 mg to 11 mg ADD;
- >11 mg to 15 mg ADD;
- >15 to 20 mg ADD; and
- >20 mg ADD.

ADD may be further stratified by (pending sufficient sample size):

- Approved indication, or by the indication groups: "PsA or RA" and "UC";
- Presence of ≥1 major VTE risk factors prior to tofacitinib initiation;
- Use of an alternative therapy (i.e., biologic) in the 12 months prior to tofacitinib initiation; and
- VTE Reporting Period (1, 2, and 3), depending on the objective.

• The operational definitions for ADD will be further elaborated in the SAP.

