A sensitivity analysis will be conducted with ADD \geq 15 mg instead of ADD > 10 mg to capture patients receiving 10 mg BID during maintenance phase. Proportions may be stratified by prior use of alternative therapy (e.g., biologic), pending sufficient sample size.

The distribution of these outcomes will be compared across the JAKi reporting periods using logistic and/or linear regression analyses.

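### 10 mg BID maintenance in UC is inferred only from average dose per 56-day block, with a main cut-off of ≥15 mg in one outcome and >10 mg in the others, and no flag for dispensed tablet strength

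*Protocol*

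**What the plan says.** Section 7 describes the recommendations by regimen: 10 mg BID as UC maintenance is restricted in patients with VTE risk factors (2019 referral), and also in those with MACE or malignancy risk factors (2022/2023 JAKi referral). It records that "Finally, in July 2018, tofacitinib 5 mg tablet BID and 10 mg tablet BID were approved by the EC" for UC. Table 1 lists 11 mg prolonged-release tablets for RA and PsA only.

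Section 9.3.3 sets the measure: "ADD will be calculated by total dose dispensed during an 8-week period divided by the length of the 8-week period, 56 days". It adds: "If a prescription spans across 2 or more 8-week periods, the dose of the prescription will be prorated across periods". Tablet strength is already an input: "Dose per prescription will be determined by the dose per tablet multiplied by the number tablets on packaging".

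The UC maintenance outcomes all look at Weeks 17–24, 25–32, 33–40 and 41–48, with these rules:

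- General UC posology row (Table 3): "tofacitinib dispensing and an ADD ≥15 mg in any of the" four intervals. The attached remark reads "Note: This definition will miss those who have one 10 mg" BID prescription when the remaining ones are 5 mg BID.
- Posology row for UC patients with VTE, CV or malignancy risk factors (Table 3): "tofacitinib dispensing and an ADD >10 mg in any of the" same intervals, with ≥15 mg as a sensitivity analysis.
- VTE UC outcome (Table 3; Section 9.7.2.4.1): >10 mg, with no alternative cut-off.
- JAKi UC outcome (Table 3; Section 9.7.2.5.1): >10 mg, with a ≥15 mg sensitivity analysis "to capture patients receiving 10 mg BID during maintenance phase".

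**The concern.** The recommendation is about a regimen, but no outcome classifies on it. Each uses a block average, and the two cut-offs err in opposite directions. At ≥15 mg, a short course can be flagged or missed depending only on where it falls on the 56-day grid. At >10 mg, anything slightly above 5 mg BID is counted, whatever tablet was supplied.

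The two posology rows share the same biologic condition and the same four blocks. The second only adds a risk factor, so its patients are a subset of the first. The subset is nevertheless judged by the looser main rule, so it can show more events than the whole. No reason is given.

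Section 7 says 10 mg BID maintenance should be kept as brief as possible, and short courses are what the ≥15 mg rule detects worst. If courses shorten over time, the ≥15 mg JAKi analysis could fall without fewer patients being exposed. The VTE UC outcome rests on >10 mg alone, so nothing shows how much of it reflects 10 mg BID.

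**Working it through.** **Inputs.** Block length 56 days and proration across blocks (Section 9.3.3); four blocks, 224 days, for Weeks 17–48 (Table 3); 10 mg BID = 20 mg/day and 5 mg BID = 10 mg/day (Section 7). The protocol gives no miss rate to reproduce. It also gives no pack size, course length or distribution of start days, so those below are assumptions.

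**The ≥15 mg rule.** With k days at 20 mg/day in a block and 10 mg/day otherwise:

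ADD = (20k + 10(56 − k))/56 = 10 + 10k/56, so ADD ≥ 15 requires k ≥ 28.

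Take one 28-day course with no gaps in cover. It is flagged only if it lies wholly inside one block, which happens for 29 of the 56 possible offsets.

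- Start uniform over a block: (56 − 29)/56 = 27/56 = 48.2% missed.
- Course wholly inside Weeks 17–48: 224 − 28 + 1 = 197 starts, of which 4 × 29 = 116 are flagged, so 81/197 = 41.1% missed.

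The same enumeration for other lengths:

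| Course at 20 mg/day | Missed, uniform over a block | Missed, wholly inside Weeks 17–48 |
|---|---|---|
| ≤27 days | 100% | 100% |
| 28 days | 27/56 = 48.2% | 81/197 = 41.1% |
| 30 days | 25/56 = 44.6% | 75/195 = 38.5% |
| 42 days | 13/56 = 23.2% | 39/183 = 21.3% |
| ≥55 days | 0% | 0% |

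**Sensitivity to the assumptions.** A 28-day course inside one block gives exactly 15.0 mg. One uncovered day in that block gives (28 × 20 + 27 × 10)/56 = 14.82 mg, so with one such day in every block 100% are missed. If fills occur every 28 days from index, they align with the blocks and 0 of 8 are missed. With 30-day fills every 30 days from index, 3 of the 7 fills lying wholly in Weeks 17–48 are missed.

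**The >10 mg rule.** With full cover, any of these courses lifts at least one block above 10 mg, so none is missed. For 28-day courses this gives 197/116 = 1.70 to 56/29 = 1.93 times as many flags as ≥15 mg, under the same assumptions. But the rule has no margin above 5 mg BID:

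- A 28-day pack of 5 mg BID holds 280 mg. Refilled every 27 days it averages 280/27 = 10.37 mg; every 26 days, 280/26 = 10.77 mg. Both exceed 10 mg with no 10 mg tablet dispensed. This assumes that the SAP does not shift early refills forward.
- 11 mg once daily gives 11 × 56/56 = 11.0 mg: flagged at >10 mg, not at ≥15 mg. The RA/PsA row avoids this by using >11 mg. The reporting bands in Section 9.3.3 run from >5 to 11 mg, so they do not separate 10 from 11 mg/day.

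**The case against.** Much of this is disclosed or partly handled. The remark in Table 3 admits the miss. It is even more pessimistic than the arithmetic, since a gap-free 28-day course inside one block does reach 15.0 mg. The risk-factor posology row and the JAKi outcome have a ≥15 mg sensitivity analysis, so a reader who infers that the two posology rows cannot be compared goes too far: they can, at ≥15 mg.

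A reader might also infer that the main tests of the 2019 and 2022/2023 recommendations lose 41–48% of 10 mg BID use. They do not. The VTE and JAKi UC outcomes use >10 mg, which catches every such course under full cover. The loss falls on the general posology row, which is only described and tabulated, and on the sensitivity analyses. Nor is that row all UC patients, since it carries a condition on biologic history.

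The 11 mg point has no known size, because nothing says how many UC-classified patients receive a product that Table 1 does not list for UC.

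Finally, strength alone would be a poor replacement for ADD. It would miss 10 mg BID supplied as 5 mg tablets. Counting any 10 mg supply that falls in Week 17 or later would also count carry-over from the induction period of up to 16 weeks. ADD is named in the objective itself (Section 8), and its operational details are left to the SAP.

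These points limit the claim. They do not explain the different main cut-offs, the missing ≥15 mg analysis for the VTE outcome, or why strength is used to compute ADD but never reported.

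**Conclusion.** The concern holds as a measurement weakness. Two facts need no assumption: the main cut-off differs between a row and its own subset, and the VTE UC outcome has no ≥15 mg analysis. It follows from the ADD formula that ≥15 mg needs at least 28 days at 20 mg/day in one block when the background is 5 mg BID, and that >10 mg leaves no margin above 5 mg BID.

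The 41–48% is an illustration, not an expected loss in this study. It requires exactly 28-day courses, uniform starts and gap-free cover; other plausible patterns run from 0% to 100%. Sustained 10 mg BID of 55 days or more inside the window is always flagged under full cover. The size of the false-positive side of >10 mg, whether from early refills or 11 mg tablets, cannot be derived from the protocol. None of this bears on which dose is right.

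**What to change.** Keep ADD and apply the following to each UC dose outcome: both posology rows, the VTE outcome and the JAKi outcome.

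1. Report beside ADD a flag for at least one dispensing of 10 mg tablets dated within Weeks 17–48. Show supply carried over from dispensings before Week 17 separately.
2. Report with it ADD ≥15 mg reached from 5 mg tablets, so that both supply routes are covered.
3. Apply >10 mg and ≥15 mg identically to all four outcomes, including the VTE one.
4. Tabulate 11 mg tablet dispensing in UC separately.

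The cost is modest extra programming and tables, since strength is already needed to compute ADD. The flag can be added in the SAP under Sections 9.3.1 and 9.3.3. Changing the main cut-offs in Table 3 may need a protocol amendment under Section 9.7 if it counts as a major change to a primary endpoint definition. One weakness remains: the 5 mg tablet component still depends on the block grid.

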In May 2019, the EC requested a reassessment of the benefit-risk of tofacitinib pursuant to Article 20 of Regulation (EC) No 726/2004 due to a signal for increased risks of pulmonary embolism (PE) and mortality arising in an ongoing Pfizer-sponsored Phase 3b/4 safety study (A3921133: Phase 3b/4 Randomized Safety Endpoint Study of 2 Doses of Tofacitinib in Comparison to A Tumor Necrosis Factor (TNF) Inhibitor in Subjects with Rheumatoid Arthritis) designed to evaluate the risk of malignancy and major adverse cardiac events in RA patients aged 50 years and older who had at least one cardiovascular (CV) risk factor. In November 2019, the Committee on Human Medicinal Products (CHMP) concluded that, based on a recommendation from the Pharmacovigilance Risk Assessment Committee (PRAC), patients treated with tofacitinib are at increased risk of venous thromboembolism (VTE) events, both for deep vein thrombosis (DVT) as well as PE, especially in patients with risk factors for VTE. The PRAC further concluded that the risk of VTE events is dosedependent. To minimise this risk, the PRAC recommended that warnings be added to the Summary of Product Characteristics (SmPC) regarding the increased risk of VTE observed in patients taking tofacitinib, especially for patients with known risk factors for VTE. The PRAC also recommended that treatment with tofacitinib be discontinued in patients with suspected VTE and that tofacitinib 10 mg BID for maintenance treatment is not recommended in patients with UC who have known VTE risk factors, unless there is no suitable alternative therapy available. Clarifications on the posology were also added, particularly for UC patients in maintenance. Specifically, some patients (i.e., patients who failed to respond to alternative treatment options for UC such as TNF inhibitor treatment) who had a reduction in response to 5 mg BID maintenance treatment may benefit from an increase in maintenance dose to 10 mg BID; for these patients, the presence of known risk factors for VTE should be considered. However, to facitinib 10 mg BID for maintenance treatment should be used for the shortest duration possible.⁴

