Initiating tofacitinib with ≥1 VTE risk factor(s)	Outcome: changes in use in patients with VTE risk factors	Defined as ≥1 VTE risk factor(s) (as listed and defined above) identified in the 12 months prior to the index tofacitinib dispensing.
Initiating tofacitinib with ≥1 VTE risk factors other than CV or malignancy risk factors	Outcome: changes in use in patients with VTE risk factors	The same definition as above but only limited to VTE risk factors other than CV or malignancy risk factors.
VTE risk factor scores	Outcome: changes in use in patients with VTE risk factors	Calculated as the sum of the number of VTE risk factors (as listed and defined above) identified in the 12 months prior to the index tofacitinib dispensing. Weighting of VTE risk factors may be considered as a sensitivity analysis to reflect the potential different
Number of UC patients with: ≥1 VTE risk factor; no prior alternative therapy (i.e., biologic); and an ADD >10 mg in Weeks 17-24, Weeks 25-32, Weeks 33-40 or Weeks 41-48 of follow-up	Outcome: changes in use in patients with VTE risk factors	importance of each risk factor. Defined as an UC patient meeting all of the following criteria: ≥1 VTE risk factor(s) (as listed and defined above) 12 months prior to the index tofacitinib prescription dispensing; 0 prescription medication dispensing for a biologic (as identified by ATC codes) in the 12 months prior to the index tofacitinib prescription dispensing; and an ADD of >10 mg in any of the intervals: Weeks 17-24, Weeks 25-32, Weeks 33-40 and Weeks 41-48 of follow-up (ADD defined in Section 9.3.3). Complete list of biologics in ANNEX 7. LIST OF ATC CODES FOR MEDICATIONS OF INTEREST TO AVOID WHILE TAKING TOFACITINIB.
Assessment of VTE risk; Section 9.3.2)	factors while receiving	tofacitinib therapy (duration of tofacitinib therapy defined in
VTE	Outcome: changes in use in patients with VTE risk factors	Defined as ≥1 ICD-10 diagnosis code for VTE while receiving tofacitinib therapy. List of VTE codes in ANNEX 12. LIST OF DIAGNOSIS CODES FOR VTE

Table 3. Operational definitions of study variables in Système National des Données de Santé

Variable	Role	Operational definition
Surgery, major	Outcome: changes in use in patients with VTE risk factors	Defined as ≥1 procedure code for a major surgery while receiving tofacitinib therapy.
MI	Outcome: changes in use in patients with VTE risk factors	Defined as ≥1 ICD-10 diagnosis code for an MI while receiving tofacitinib therapy.

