9.7.2.4.1. Patients with venous thromboembolism risk factors

To describe changes in the utilisation of tofacitinib, this analysis will be stratified by the VTE reporting periods 1, 2 and 3.

The proportion of patients with one or more risk factors for VTE, identified prior to tofacitinib initiation, will be described and tabulated overall and by individual VTE risk factor (e.g., prior VTE and recent MI).

Logistic regression analyses will be used to calculate odds ratios along with their corresponding 95% confidence intervals and p values to formally compare the proportion of patients with VTE risk factors across VTE reporting periods 1, 2 and 3.

To enhance statistical power in detecting changes, a composite score for the VTE risk factors will also be generated by summing the individual VTE risk factors. Linear regression analyses will be employed to compare the VTE composite score across the VTE reporting periods. In addition to the summed composite score, the same analysis using a composite score weighting the risk factors may be considered in an exploratory fashion (weights will be developed and described in the SAP). Regression coefficients with their 95% confidence intervals and p values will be generated.

The proportion of patients diagnosed with UC, one or more VTE risk factors identified prior to tofacitinib initiation and no use of alternative therapy (i.e., biologic) prior to tofacitinib initiation whose ADD in Week 17 through Week 24, Week 25 through Week 32, Week 33 through Week 40 or Week 41 through Week 48 was >10 mg will be described and tabulated.

The proportion of patients who discontinue or continue to facitinib after developing one or more VTE risk factors while taking to facitinib will be described separately.

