high validity since they are specifically requested by the physician for full reimbursement of care linked to the condition. Hospital discharge diagnoses are also expected to have high validity. Furthermore, misclassification of indications as an off-label indication when no diagnosis codes for RA, PsA or UC are identified during the time window will primarily impact sample size (and thus precision of estimates) of the RA, PsA or UC groups when evaluating the adherence of prescribers to aRMM materials, but are not expected to materially bias the results.

Duration of tofacitinib treatment and posology

Because automated health databases often do not record the intended duration of use of a dispensed prescription (i.e., days of supply), a proxy for days' supply is developed based on package size and time between reimbursed prescriptions and will be further detailed in the SAP. As such, calculated ADD would reflect the actual use of tofacitinib by patients if the patients did not take the drug as prescribed. Though this approach is commonly applied in the SNDS, to minimize potential misclassification of drug exposure, a series of checks will be undertaken, such as comparisons with recommended posology, the review of overlapping reimbursements and frequency of reimbursements over pre-specified time-periods.²⁵⁻²⁷

Adherence to the SmPC recommendation of "if no suitable treatment alternatives are available"

The alternative "no prior use of an alternative therapy (i.e., biologic)" is used as a proxy to measure adherence to the SmPC recommendation of "if no suitable treatment alternatives are available" due to constraints with the SNDS claims data source in which "suitability" of a treatment is not documented. A limitation associated with use of this proxy method is a possible overestimation of the non-adherence to the recommendations for limitations of use, which may lead to a conversative estimate of the effectiveness of aRMMs. For example, if a patient older than 65 years initiated tofacitinib because his/her prescriber thought all other therapies were unsuitable and did not prescribe other therapies prior to tofacitinib initiation, this event will be falsely counted as non-adherence to the recommendations for limitations of use (and thus undermining the effectiveness of aRMMs), because no prior use of an alternative therapy was identified from claims data.

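### Two UC posology-adherence outcomes in Table 3 are named for patients with no prior biologic but defined as requiring at least one

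*Protocol*

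**What the plan says.** Table 3 (Section 9.3.1), under adherence to the recommended posology, has two rows for UC patients. The name of each ends by restricting it to patients with a UC diagnosis and no biologic before tofacitinib initiation.

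- **First UC row.** The definition opens "Among UC patients, is defined as ≥ 1 prescription dispensing" of a biologic before the "tofacitinib dispensing and an ADD ≥15 mg in any of the" listed maintenance intervals (Weeks 17-24, 25-32, 33-40 or 41-48).
- **Second UC row.** The opening is the same, with ADD >10 mg in any of those intervals up to "Weeks 41-48 of follow-up and ≥1 VTE, CV or malignancy" risk factor from baseline to Week 16. A sensitivity analysis repeats this definition with ADD ≥15 mg.

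The UC/VTE row later in the same table requires "0 prescription medication dispensing for a biologic (as identified by ATC codes) in the 12 months prior to the index tofacitinib prescription dispensing". Its analysis text in Section 9.7.2.4.1 specifies "no use of alternative therapy (i.e., biologic) prior to tofacitinib initiation whose ADD in Week 17 through Week 24" and the later intervals. Section 9.9.1.1 explains that a patient is counted as non-adherent "because no prior use of an alternative therapy was identified from claims data".

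Section 9.7.2.1 commits to describing and tabulating all the posology-adherence variables in Table 3.

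**The concern.** The operational-definition column is what a programmer implements. Followed literally, it produces a table whose label says biologic-naive and whose content is biologic-experienced. The patients the rows are meant to find, those on a high maintenance dose without having tried a biologic, would be left out. A regulator reading the result as evidence on adherence to the risk minimisation measures would be reading a figure for the complementary group.

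The group captured is also the one with the better claim to the higher dose. Section 7 says the later posology clarification foresaw possible benefit from 10 mg BID maintenance for "patients who failed to respond to alternative treatment options for UC such as TNF inhibitor treatment" whose response fell on 5 mg BID.

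**Working it through.** The plan gives no figure to reproduce. This is a check of definitions, plus one identity for size.

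**1. Name against definition.** Let B be the number of biologic dispensings before index.

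| Outcome (Protocol) | Name | Operational condition |
|---|---|---|
| UC, ADD ≥15 mg (Table 3, posology) | B = 0 | B ≥ 1 and dose |
| UC, ADD >10 mg with risk factor (Table 3, posology) | B = 0 | B ≥ 1 and dose and risk factor |
| Sensitivity analysis of the row above, ADD ≥15 mg | B = 0 | inherits B ≥ 1 |
| UC/VTE, ADD >10 mg (Table 3; Section 9.7.2.4.1) | B = 0 | B = 0, 12 months |
| CV factor, no prior alternative (Table 3) | B = 0 | B = 0, 12 months |
| Malignancy factor, no prior alternative (Table 3) | B = 0 | B = 0, 12 months |
| Continuing after turning 65, no prior alternative (Table 3) | B = 0 | B = 0 |
| Continuing after turning 65, with prior alternative (Table 3) | B ≥ 1 | B ≥ 1 |

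For the same window, {B = 0} ∩ {B ≥ 1} is empty. In the first three lines the overlap between patients named and patients counted is therefore 0%, whatever the data show.

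**2. Which side is wrong.** Elsewhere the table uses zero dispensings for a no-prior-biologic name and at least one for a prior-biologic name. Section 9.9.1.1 makes absence of a prior biologic the proxy for non-adherence. The row names agree with both, so the error lies in the two definitions.

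**3. Size.** Let b be the biologic-experienced share of UC patients who otherwise meet the row. Then reported count / intended count = b / (1 − b). The protocol does not give b; the range below is an assumption.

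- b = 0.3: 0.3/0.7 = 0.43
- b = 0.5: 0.5/0.5 = 1.0
- b = 0.7: 0.7/0.3 = 2.3
- b = 0.9: 0.9/0.1 = 9.0

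The count may be too low or too high. At b = 0.5 it would look right while describing entirely different patients.

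**4. Are all the captured patients wrongly scored?** No.

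- At initial approval the UC doses were "10 mg BID for induction (up to a 16-week period) and 5 mg BID for maintenance, which should not be exceeded", with no exception stated for biologic-experienced patients. The revisions that introduced the allowance were approved on 31 January 2020 (Section 7). UC patients can index from May 2019, and Week 17 begins after 16 × 7 = 112 days. A patient indexing on 1 May 2019 enters maintenance on 21 August 2019, before that approval.
- After that date, Section 7 still advises against 10 mg BID maintenance in UC patients with VTE risk factors unless no suitable alternative exists. Having used one biologic does not settle that question.

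**The case against.** Four defences deserve an answer.

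- **The phrase only defines what an alternative therapy is.** A parenthesis in Section 9.7.2.4.2 does use the at-least-one wording in that way. In these two rows, however, it is the first condition of the patient-level outcome, joined by 'and' to the dose. This defence fails.
- **The intent is plain and the SAP can settle it.** The intent is indeed plain from the names and the parallel rows. Section 9.3.1 lets the SAP refine algorithms and code lists, but a condition that reverses its own variable name is a misstatement, not a detail left open.
- **Other outcomes carry the information.** This stands in part. The UC/VTE row covers VTE factors at >10 mg. The JAKi outcome covers CV and malignancy factors, with a ≥15 mg sensitivity analysis; Table 3 says it will be stratified by prior biologic, Section 9.7.2.5.1 only that it may be. Section 9.3.3 allows ADD to be split by indication and prior biologic, but this is optional and uses a category starting above 15 mg. No mandatory outcome reproduces the general ≥15 mg row.
- **The missing look-back is not a real gap.** This largely stands. Section 9.2.3 sets a 12-month baseline for prior medication, and Table 3 defines prior use of any biologic over 12 months. Writing the window into the two rows is for consistency.

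A reader might infer that every patient these rows capture is misscored, at all dates. The documents do not support that, as step 4 of the working shows. A reader might also object that the >10 mg row pools VTE, CV and malignancy factors over all index dates. That is not pressed: the UC/VTE outcome is already split by VTE reporting period and the CV/malignancy dose outcome by JAKi reporting period.

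**Conclusion.** The two definitions are wrong as written and should be corrected. The error is a contradiction with the row names and with the non-adherence proxy in Section 9.9.1.1; it does not show that all the captured use was within posology. Zero overlap between named and counted patients follows from the wording alone, given a common look-back. The ratios of 0.43 to 9.0 rest on an assumed biologic-experienced share and show only that the error could run in either direction.

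Three outputs are affected: the two rows and the ≥15 mg sensitivity analysis. All are descriptive. The sample-size tables and the regression comparisons across reporting periods are untouched.

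**What to change.** In both UC posology rows of Table 3, replace the requirement of at least one biologic dispensing before index with zero biologic dispensings in the 12 months before the index tofacitinib dispensing, as in the UC/VTE row. The sensitivity analysis then follows without further change.

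The cost is one condition in two rows and the matching program lines. Because the rows sit under Primary Objective 2, the correction belongs in the protocol text as well as the SAP; Section 9.7 calls for an amendment when primary endpoint definitions undergo major modification. The drawback is that a patient whose biologic failure is older than 12 months will be counted as non-adherent. That is an overestimate of the kind Section 9.9.1.1 already accepts for this proxy.
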